Viral spread (for both outcomes)	Total lockdown Partial lockdown (geographical, step-wise/graduated response) Curfew School closure Closure of shopping malls, gyms, churches, parks Remote work Restrictions to national/subnational mobility Prohibition of mass gatherings
Health systems response (for COVID-19 deaths outcome)	Interventions to increase testing capacity Interventions to increase the number of ICU/critical beds
Mitigation strategies (for both outcomes)	Direct social assistance (in-kind/cash) Cash transfer Withdrawal of pension funds

Comparator

In an interrupted time series analysis, the comparator is a counterfactual outcome defined as the projection of the pre-intervention trend to simulate what would have happened if the policy had not occurred (see Statistical Analysis Plan for definitions).

Outcomes

We will assess three primary outcomes. The first outcome will be the 7-day moving average of daily confirmed cases of COVID-19/SARS-CoV-2. The second outcome is the time-varying reproductive number between the current and previous period.¹⁹ The third outcome is the 7-day moving average of the daily number of deaths by COVID-19 in Latin American subnational regions. For the statistical modelling, these averages will be rounded to the nearest integer. We will consider a 7-day lag as the primary lag. Details on sensitivity analyses can be found in the Statistical Analysis Plan.

We define the outcomes following the official national sources definitions, as each country applies its criteria to define the occurrences and the deaths caused by COVID-19. It is important to note that those criteria are not always clearly stated, but all subnational units are under the same measure at each time.

Data sources

We will obtain COVID-19 cases and deaths data, as well as the covariates, on official government sources, such as the Ministry of Health and Ministry of Science and Technology (see Supplementary Appendix Table S2). The intervention information will come from legal documents, official statements, and quantitative accounts from trustable sources.

Covariates

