## Introduction

The COVID-19 pandemic is evolving quickly globally. By January 22, 2021, there were more than 112 million reported cases and more than 2.6 million deaths worldwide. Latin America is one of the worst-hit regions and accounts for 20.3% of the SARS-COV2 cases and 30% of the global deaths, despite having only 8% of the global population. The effectiveness of policies to reduce the spread of COVID-19 has been analyzed in several empirical studies. Nevertheless, few of these studies have included countries in Latin America or examined the effect heterogeneity and potential explanations for it. In this study we aim, first, to estimate the effectiveness of nonpharmaceutical interventions on SARS-COV2 transmission and COVID-19 mortality in Latin America; second, to examine the effect heterogeneity of transmission and mortality at the local level. Third, assuming we find evidence of moderate to substantial heterogeneity at the local level, we aim to explore potential explanations for this heterogeneity.

This Statistical Analysis Plan (SAP) provides an in-depth description of the statistical methods and definitions for the study analysis. More information on the rationale and data sources can be found in the Study Protocol.

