### *Timing of analyses and outcome assessments*

We will use data from the date of the first case in each country until December 31, 2020. We will use publicly available daily data for all outcomes. We will use the enforcement date on data on interventions collected from PoliMap ([www.polimap.org](http://www.polimap.org)).

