Assumption 2. We will explicitly incorporate co-occurring interventions in a seven-day period as a combination of interventions. We will also adjust for changes in the case definition of COVID-19 cases and deaths for each of the respective outcomes. We will report in the Supplementary Appendix the exact dates considered in the analysis for each country/subnational unit and the interventions included in each intervention period.

Assumption 3. We will introduce flexible spline functions to account for seasonality and long-term trends. We will add a scale parameter, which will be the Pearson statistic divided by the residual degrees of freedom, to account for potential overdispersion (a violation of the Poisson regression assumption). We will test for autocorrelation using the Durbin-Watson tests and visual plots of the autocorrelation function and partial autocorrelation function. If there is evidence of autocorrelation, we will use the Newey-West method to obtain adjusted standard errors.

Therefore, in the final analysis, we will use Poisson regression to model the count data.. The final model is an extension of the regression described in equation 1 with the specifications described above. The model will include each of the interventions (either as single interventions or combinations of), denoted  $j = 1, \dots, J$ . This method allows estimating simultaneously the effect of several interventions. We will consider interventions implemented within a 7-day period as a combination of interventions, following previous studies. This means that the maximum number of combinations of interventions is 52,  $t = 1, \dots, 52$ . We will estimate the effect of the interventions separately when interventions are separated by at least seven consecutive days and for a maximum period of 30 days. The primary analysis will include a 7-day lag to account for the delay in the intervention to be effective, considering the incubation period of SARS-COV2.

$$(5) \ln(Y_t) = \beta_0 + \beta_{1j}time_{tj} + \beta_{2j}post_{tj} + \beta_{3j}timepost_{tj} + \mu_t$$

This model will be run at the municipal level and, therefore, we expect to run 10,000 regressions multiplied by the number of combinations of interventions at each municipal level. Coefficient  $\beta_{3j}$  is the coefficient of interest and represents the change in slope after the intervention  $j$  at period  $t$ .

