In coefficient of interest at a second stage, we will pool the effects for each intervention -or combination of interventions- (i.e. the coefficient of interest  $\beta_{3j}$  from the local level regression) using a random-effects meta-analysis. This meta-analysis will provide information to obtain a pooled effect estimate and a measure of heterogeneity. We will use the  $I^2$  as a measure of heterogeneity.

If the heterogeneity is moderate or high ( $I^2$  higher than 50%), we will carry out a meta-regression to assess whether subnational level determinants can explain the observed heterogeneity. We will analyse the following covariates: (i) Population size, (ii) Population density, (iii) Proportion of population over 60 years old, as a proxy for age structure of the population, (iv) Household density, and (iv) Proportion of population with basic education, as a proxy of socioeconomic status.

The meta-regression has the effect size  $\widehat{\theta}_k$  of a first-stage regression  $k$  as the outcome, covariates  $x_{ik}$ , a fixed effect  $\rho_1 S_a$  for the second-tier level  $a$  (i.e. State or Region) and a random-effect  $\delta_2 N_b$  for the national level  $b$  and a fixed effect  $\rho_2 Y$  for the time of the year (quarterly periods)(equation 6). The equation includes two types of independent errors, where  $\varepsilon_k$  is the sampling error of the effect size and  $\varsigma_k$  is the random-effect error term.

$$(6) \theta_k = \gamma_1 x_{1k} + \dots + \gamma_n x_{nk} + \rho_1 S_a + \delta_2 N_b + \rho_2 Y + \varepsilon_k + \varsigma_k$$

These controls for higher levels of administration and time of the year will allow us to control for constant characteristics at the subnational and national level, as well as changes in the effectiveness throughout the pandemic.

We will carry out the following sensitivity analyses: (1) comparison of effect estimates using a 5-day and 10-day lag; (2) quasi-myopic analyses to control for anticipatory effects (if there is evidence of), and (3) placebo tests evaluating changes at times when no policy was implemented. In the analyses for the number of cases and time-varying R, we will run additional sensitivity analyses estimating the number of SARS-CoV-2 cases corrected by under-ascertainment derived from mortality statistics.

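### Equation 6 makes no allowance for several effect estimates from one municipality, so wherever a municipality repeats within one meta-regression the standard errors of the five municipal covariates are wrong, mostly too small.

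*SAP*

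**What the plan says.** The third aim is conditional: if local effects differ enough, "we aim to explore potential explanations for this heterogeneity" (SAP, Introduction). The tool is the meta-regression in equation 6 (SAP, Analysis methods), run only when I² exceeds 50%.

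- **Record.** The outcome is the effect size "of a first-stage regression", indexed by k, not one value per municipality.
- **Structure.** There is a fixed effect for state or region, a random effect for country and a fixed effect for quarter. The SAP then says "The equation includes two types of independent errors": sampling error and random-effect error, both indexed by k.
- **Covariates.** The five covariates are population size, population density, share over 60, household density and share with basic education. The Protocol (Covariates) draws them mainly from the latest census and a 2020 population projection, so each has one value per municipality.
- **Number of estimates.** The SAP says "we expect to run 10,000 regressions multiplied by the number of combinations of interventions at each municipal level", and of the first-stage model that "This method allows estimating simultaneously the effect of several interventions".
- **Pooling.** The meta-analysis pools separately for each intervention or combination. The SAP does not say whether equation 6 is also fitted that way, and equation 6 has no term for intervention type.

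No passage gives a municipality term, a covariance among estimates from one municipality, or clustered standard errors for the second stage. Newey-West applies to the first-stage standard errors only, and none of the listed sensitivity analyses covers this dependence.

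**The concern.** Two estimates from the same municipality are unlikely to be independent, even given state, country and quarter. There are two sources of dependence, with opposite signs.

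- **Shared true effect.** If a municipality responds more or less strongly to policies in general, its estimates are positively correlated.
- **Shared data.** If successive policies are fitted jointly to one series, the slope after the first policy is also the slope before the second. The sampling errors of neighbouring slope changes are then negatively correlated.

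A covariate that does not vary within a municipality takes the full effect of the net correlation, and state effects do not remove it. At stake are the standard errors behind the third aim. If they are too small, density or schooling is called explanatory too often; if too large, a real gradient may be missed.

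**Working it through.** The plan gives no standard error, significance level or power for the meta-regression, so there is no figure to reproduce.

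**Step 1: can a municipality repeat within one fit?**

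- *Fitted across interventions:* yes, for every municipality with more than one intervention period.
- *Fitted per intervention:* only if the same intervention or combination recurs. The SAP defines the coefficient of interest by intervention and by period, which allows this. Protocol Table 1 puts "Partial lockdown (geographical, step-wise/graduated response" under one label. On timing, "We will use data from the date of the first case in each country until December 31, 2020", while each effect is estimated over at most 30 days. Recurrence is plausible but not stated.

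**Step 2: sampling correlation of neighbouring slope changes.** Take a joint segmented fit with a level jump, equal segments and independent errors. Each segment slope s then has the same variance v and is independent of the others.

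- Var(s₂ − s₁) = 2v
- Cov(s₂ − s₁, s₃ − s₂) = −v
- Correlation = −v/2v = −0.50

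Non-neighbouring changes correlate 0. Exact least-squares results for segments of 7, 14 and 30 days, with and without the jump and with independent or AR(1) 0.8 errors, give −0.50 to −0.72 for neighbours.

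**Step 3: effect on the standard error.** Assume m records per municipality, equal weights, and variances M (shared within the municipality), E (specific to the episode) and S (sampling). Let c be the mean sampling correlation over pairs. With −0.50 for neighbours, c = −0.50 for m = 2. For m = 3, two of the three pairs are neighbours, so c = −1/3.

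- ρ = (M + cS)/(M + E + S)
- true SE / naive SE = √(1 + (m − 1)ρ)
- type I error = 2[1 − Φ(1.96 / ratio)]
- I² is about (M + E)/(M + E + S)

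Assumed inputs are M = E = 0.5, S = 1 (I² 50%, half shared); M = E = 1.5, S = 1 (I² 75%, half shared); M = 0.1, E = 0.9, S = 1 (I² 50%, one tenth shared); and SDs of 0.03 (municipality) and 0.02 (episode) with SE 0.015. The last gives I² = 0.0013/0.001525 = 85%, with 0.0009/0.0013 = 69% shared.

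| m | I² | shared | ρ | SE ratio | type I error |
|---|---|---|---|---|---|
| 1 | any | any | – | 1.00 | 5.0% |
| 2 | 50% | half | 0.00 | 1.00 | 5.0% |
| 3 | 50% | half | 0.083 | 1.08 | 7.0% |
| 3 | 75% | half | 0.292 | 1.26 | 11.9% |
| 2 | 85% | 69% | 0.516 | 1.23 | 11.1% |
| 3 | 85% | 69% | 0.541 | 1.44 | 17.4% |
| 2 | 50% | one tenth | −0.200 | 0.89 | 2.8% |
| 3 | 50% | one tenth | −0.117 | 0.88 | 2.5% |

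In the second row the two sources cancel exactly. If the repeats are not neighbours in time, c = 0; the half-shared case at I² 50% then has ρ = 0.5/2 = 0.25 and type I error of 8.0% (m = 2) or 11.0% (m = 3).

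**Step 4: simulation.** Equation 6 was simulated with state and quarter fixed effects, 600 municipalities, 30 states and 2,000 runs per setting.

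- m = 3, I² 50%, half shared: 6.8%
- m = 3, I² 75%, half shared: 13.6%
- m = 3, I² 50%, one tenth shared: 1.8%
- one record per municipality: 5.6%

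Standard errors clustered by municipality gave 4.8% to 5.7% in all eight settings tried. A separate simulation at I² near 85% gave 11% (m = 2) and 17% (m = 3), against about 5% with clustering.

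**The case against.** The strongest objection is that the plan never says a municipality enters the same meta-regression twice. The meta-analysis is per intervention, and equation 6 may follow it. The quarter term is no proof of repeats, because municipalities adopt the same policy at different dates. Table 1 is a list of categories and does not make each lockdown step a record. A recurrence with different accompanying measures is a different combination and goes to another pool. All this stands: repeats are likely but not established, and the point is conditional on them.

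Three stronger readings are tempting, and the documents do not support them.

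- *That the plan treats all estimates as independent.* It treats them as independent given state, country and quarter. The sentence on errors can also mean only that sampling error and random-effect error are independent of each other, which a corrected model still needs.
- *That real gradients would be badly missed where sampling error dominates.* The I² threshold largely excludes this. With an SE of 0.04 and both true SDs at 0.01, I² is 0.0002/(0.0002 + 0.0016) = 11%, and the meta-regression would not run.
- *That the negative correlation always applies.* It needs a joint first-stage fit and neighbouring policies in the same pool. The SAP is unclear on joint fitting, since it speaks both of simultaneous estimation and of regressions multiplied by the number of combinations.

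The third aim is also exploratory and conditional. That limits the consequence, but does not make a wrong standard error right.

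**Conclusion.** The point holds in conditional form. The omission is certain: equation 6 has neither a municipality term nor a clustered standard error, and every covariate it tests is fixed within a municipality. If any municipality supplies more than one record to a fit, the covariate standard errors are in general wrong.

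The likelier direction is too small, because the meta-regression runs only when true effects vary substantially. For three records the net correlation is positive once the shared variance exceeds one third of the sampling variance. The conservative error is mild and arises near the 50% threshold with little sharing.

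The sizes are scenarios, not predictions. They rest on assumed numbers of repeats, variances, correlations, equal weighting and a 5% test level, none of which the documents give. Opposing correlations can cancel. With one record per municipality nothing is wrong.

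**What to change.** 1. State whether equation 6 is fitted per intervention or across interventions, and report how many municipalities supply more than one record to each fit.
2. Report covariate standard errors clustered (cluster-robust) by municipality. This is the essential part: a random-intercept variance cannot be negative, so an intercept alone cannot represent net negative dependence.
3. Where repeats occur, add a municipality random intercept nested in state.
4. Reword the sentence on errors: keep the independence of sampling error from random-effect error, without implying that estimates from the same municipality are independent of each other.

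No new data are needed. The cost is one model term and one variance option, after checking that the meta-regression routine named under Statistical software accepts both. Covariate intervals may be noticeably wider where repeats are common and effects are shared (by a factor of about 1.2 to 1.4 in the I² 85% rows above), and should change little otherwise. In fits with few municipalities, clustered errors can stay slightly liberal: runs with 150 municipalities gave 6% to 8%. A small-sample correction is sensible there.

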#### *Statistical software*

We will use R (current version 3.6.3) for all analyses. We will use the *glm* function to run the Poisson model, using the code developed by Gasparrini et al as a reference source and the *metareg* package for the meta-regression. Under-ascertainment will be estimated using code developed by Russell et al as a reference.

